#### 4.9. Anti-alirocumab Anti-body Variables

Anti-drug (alirocumab) antibody (ADA) are assessed at baseline (before the first study treatment injection), at week 12/or end of double-blind treatment visit, and week 24/or end of open-label treatment visit. ADA measurements will be assigned to similar analysis windows as defined for efficacy endpoints in [Appendix 10.2](#). As appropriate, patient frequencies and percentages will be depicted, and the percentages will be calculated based on the ADA population for the analysis of the double-blind period and based on the OLE population for the analysis of the open-label period.

The following variables will be described:

- ADA response (Positive or Negative). For ADA positive:
  - Titer levels
  - Neutralizing status (Positive or Negative)
- Pre-existing positive ADA defined as patients with positive ADA response at baseline with less than 4-fold increase in titer in the post-baseline period
- Treatment-emergent positive ADA response defined as 1) Patients with no ADA positive response at baseline but with any positive response in the post-baseline period or 2) Patients with a positive ADA response at baseline and at least a 4-fold increase in titer in the post-baseline period. For treatment-emergent positive ADA, the following categories for ADA duration will be applied for the analysis of the double-blind period:
  - A persistent positive response is a treatment-emergent ADA positive response detected in at least 2 consecutive post-baseline samples separated by at least a 12-week period
  - An indeterminate duration positive response is defined as ADA present only at the last sampling time point
  - A transient positive response is defined as any treatment-emergent positive ADA response that is neither considered persistent nor indeterminate

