#### 5.9. Analysis of Anti-alirocumab Antibody Variables

The summary of ADA variables will be presented separately for the double-blind and open-label period. The double-blind period will be presented by treatment groups (alirocumab, placebo) on the ADA population. The open-label period will be presented by all patients and by treatment group of the double-blind period (i.e., alirocumab, placebo) on the open-label population. No

formal inferential testing will be performed for either period. Summaries will be descriptive in nature.

ADA variables will be summarized, taking into account all samples regardless of timing in relation to injections. ADA results will be summarized as follows:

- ADA results (negative or positive) by time point
- Neutralizing status (negative or positive) by time point for positive ADA
- ADA titers using descriptive statistics (median, minimum and maximum) for positive ADA by time point
- Number (%) of patients with pre-existing ADA and number (%) of patients with treatment-emergent ADA positive response
- Number (%) of patients with persistent/indeterminate/transient treatment-emergent ADA positive response (only for the double-blind period)
- Time to onset of treatment-emergent ADA positive response using descriptive statistics.

Correlations between ADA parameters (e.g., titers, treatment-emergent ADA positive status, neutralizing status) and safety and/or efficacy endpoints will also be explored (e.g., scatter plot).

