## 6.5. Visit Windows for Time Points

Visit windows will be programmatically imposed on those efficacy and safety measures repeatedly collected over the course of the study. These visit windows are derived from the number of days in study, specifically assigning day ranges to mimic the study assessment schedule provided in the protocol. Data analyzed by time point (including efficacy, laboratory safety data, vital signs, ECG, quality of life, PK and ADA) will be summarized using the analysis windows given in [Appendix 10.2](#). These analysis windows will be applicable for all analyses, and they are defined to provide more homogeneous data for time point-specific analyses. If multiple valid values of a variable exist within an analysis window, the nearest from the targeted study day will be selected. If the difference is a tie, the value after the targeted study day will be used. If multiple valid values of a variable exist within a same day, then the first value of the day will be selected when time is available, else the scheduled visit will be selected.

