**Table 1a Analysis Windows Definition for Double-Blind Period – All Endpoints Except Vital Signs**

Time point	Targeted study day	Analysis window in study days
Week 4	29	15 to 42
Week 8	57	43 to 70
Week 12	85	71 to minimum of: 98 OR study day corresponding to the first open-label injection for patients entering open-label period

Study days are calculated from the day of first double-blind IMP injection, the day of first double-blind IMP injection being Day 1. For randomized but not treated patients, Day 1 is the day of randomization.

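### The antibody-duration split is confined to a period with one scheduled post-baseline sample, so on the planned schedule its persistent category is empty by design

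*SAP*

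**What the plan says.** SAP 4.9 schedules ADA samples at baseline ("before the first study treatment injection), at week 12/or end of double-blind treatment visit, and week 24/or end of open-label treatment visit"). Protocol Table 1 agrees: ADA is marked at baseline, visit 6 (week 12) and visit 8 (week 24), and at no visit between.

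For treatment-emergent positives, SAP 4.9 states that "the following categories for ADA duration will be applied for the analysis of the double-blind period":

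- Persistent: "detected in at least 2 consecutive post-baseline samples separated by at least a 12-week period".
- Indeterminate: "An indeterminate duration positive response is defined as ADA present only at the last sampling time point".
- Transient: "A transient positive response is defined as any treatment-emergent positive ADA response that is neither considered persistent nor indeterminate".

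SAP 5.9 lists the output as "Number (%) of patients with persistent/indeterminate/transient treatment-emergent ADA positive response (only for the double-blind period"), and presents the open-label period separately.

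On which samples count, SAP 4.9 assigns ADA results to windows similar to the efficacy windows. SAP 6.5 names ADA among the data summarised by time point and adds: "These analysis windows will be applicable for all analyses". In Table 1a the first window opens on Day 15, and the week 12 window runs "71 to minimum of: 98 OR study day corresponding to the first open-label injection for patients entering open-label period". SAP 5.9, however, also says that ADA summaries use every sample whatever its timing relative to an injection.

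**The concern.** The definition of persistent needs two post-baseline samples 12 weeks apart, and the period it is applied to supplies one. The scheduled pair that would fit, week 12 and week 24, straddles the two periods, and the split is not applied to the open-label period.

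SAP 7 says the first-step analysis will support the submission to health authorities. A row reading 0% persistent in that analysis could be taken as a finding about alirocumab's immunogenicity when the sampling schedule fixed it in advance. A second weakness is that transient is defined by exclusion. A patient can receive that label without any sample showing that the antibodies went away.

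**Working it through.** The plan gives no figure to reproduce here. The check is day arithmetic plus a walk through the three definitions.

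**1. Day convention.** The schedule places week w on Day 1 + 7w: week 12 = 1 + 84 = Day 85 and week 24 = 1 + 168 = Day 169, both as in protocol Table 1. Twelve weeks is therefore a difference of 84 days.

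**2. Planned schedule.** Post-baseline ADA samples in the double-blind period: one (week 12). One sample makes no pair, so persistent cannot occur.

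**3. Unscheduled samples inside the Table 1a windows.** The windows run from Day 15 to Day 98 at the latest, and close at the first open-label injection if that is earlier.

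| Week 12 window closes on | Widest possible gap | Required |
|---|---|---|
| Day 98 | 98 − 15 = 83 days | 84 |
| Day 85 (planned open-label start) | 85 − 15 = 70 days | 84 |

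No pair of days inside the windows reaches 84.

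**4. Samples outside the windows.** Protocol 7.4.2 gives a patient who stops double-blind drug an extra visit with the end-of-double-blind assessments, which include ADA. The patient then returns to the original schedule.

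- Early sample: for a gap of 84 days to a week 12 sample on Day 88 (the late edge of ±3 days), it must fall by Day 88 − 84 = 4. For a sample on Day 98, it must fall by Day 98 − 84 = 14. Both precede the first window.
- Week 24 sample from a discontinuer who never starts open-label drug: 169 − 85 = 84 days after week 12, nominally just enough, but beyond Day 98.

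**5. Which label each patient gets.**

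- Baseline negative, on schedule, positive at week 12: positive only at the last double-blind sample, so indeterminate. That is a fair label.
- Early discontinuer, positive at an extra sample on Day 15 to 70 and again at a week 12 visit on Day 82 to 88: the gap is between 82 − 70 = 12 and 88 − 15 = 73 days. The response is not persistent, and it is not confined to the last sample. If no later sample counts, it is transient by exclusion, with no negative result after baseline.
- Baseline positive, with at least a 4-fold titer rise at week 12: treatment-emergent by SAP 4.9. Read literally, ADA was also present at baseline, so it was not present only at the last time point, and there is one post-baseline sample. The response again falls to transient.

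**6. The pair that could carry the definition.** Week 12 to week 24 is nominally 169 − 85 = 84 days. With ±3 days at each visit the actual gap runs from 166 − 88 = 78 to 172 − 82 = 90 days.

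**The case against.** The best counter-argument concerns which samples count. The duration label is a patient-level class over post-baseline samples, whereas SAP 6.5 introduces the windows for data analysed by time point and SAP 4.9 calls the ADA windows only similar to the efficacy ones. SAP 5.9 then admits all samples regardless of injection timing. On that reading the off-window routes in step 4 are open and persistent is attainable in rare cases. This stands in part: the SAP 5.9 sentence is about injections and does not clearly override the windows, but the SAP does not close the question. A reader might infer that persistent is impossible for any patient. The documents do not support that; they support impossibility on the planned schedule and, if the windows govern, between in-window samples.

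A reader might also infer that every early discontinuer who is positive twice will be called transient. That does not follow either, because protocol 7.4.2 keeps such a patient on schedule and a week 24 sample is then due. If that sample counts, the label may change.

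An inclusive count gives 98 − 15 + 1 = 84 days and would appear to rescue the in-window case. The documents count by difference, with Day 1 to Day 85 being 12 weeks, so it does not.

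Finally, the effect is slight. Indeterminate is the right word for a single positive at the last sample, and results by time point are reported alongside, so a careful reader could see that there was one post-baseline visit. That limits the severity; it does not give the persistent row any content.

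**Conclusion.** The point holds and is minor. On the planned schedule the double-blind table must show 0% persistent, and nearly every treatment-emergent positive will be indeterminate. Within the Table 1a windows the shortfall is at least one day (83 against 84), and 14 days when open-label dosing starts on Day 85. The in-window statement rests on the windows governing the duration class, which SAP 4.9 and 6.5 suggest but SAP 5.9 leaves open.

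The transient label can be attached to patients with no negative post-baseline result. Few patients, possibly none, would be affected. The documents give neither an ADA-positive rate nor a rate of early stopping with continued sampling, so no reliable count can be stated.

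It would be wrong to read this as a fault in the immunogenicity assessment as a whole. Treatment-emergent incidence, titers, neutralizing status and results by time point do not use the split. The ADA summaries are descriptive, and no endpoint or test depends on them.

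**What to change.** Delete the double-blind duration categories from SAP 4.9 and the matching line from SAP 5.9. Protocol 4.4 and 10.4.7 ask for no duration category, so the protocol needs no change, and the cost is SAP wording only. There is a precedent: SAP 1.2.3 drops the new-onset-diabetes analysis because its definition does not suit a study this short.

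If duration is still wanted, report it only in the second-step analysis, for patients randomised to alirocumab, from the week 12 and week 24 samples already planned. Define persistence by visit rather than by a strict 84-day gap, since actual gaps can be as short as 78 days. Require a later ADA-negative sample for transient, not merely a titer that has fallen below the 4-fold threshold. State explicitly whether samples outside the analysis windows count.

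This option has three costs: no placebo comparison, because placebo patients receive alirocumab from week 12; later reporting; and a visit-based criterion in place of the exact 12-week one.

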#### 4.10. Pharmacokinetic (PK) Variables

Samples of drug concentration measurements are collected at baseline (week 0), weeks 4, 8, 10, 12, and 24.

Pharmacokinetic variable is the total alirocumab concentration at each time point. Alirocumab concentration, total and free PCSK9 concentration will be described following time windows as defined in [Appendix 10.2](#) .

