## 5.10. Analysis of Pharmacokinetic Data

Concentrations of total alirocumab in serum and total and free PCSK9 concentrations will be summarized on the PK population by treatment group and visit using descriptive statistics. Descriptive statistics could be provided by specific sub-groups (e.g., gender, BMI, age), as needed.

Time profile for concentrations of total alirocumab and total and free PCSK9 will be provided by treatment group using graphs (mean  $\pm$  SD or Median, as appropriate). Plots of the individual concentrations of alirocumab, and total and free PCSK9 may be presented versus actual time. Additional plots will be prepared, as deemed necessary (e.g., to explore the relationship with some safety or efficacy endpoints of interest).

Concentrations of total alirocumab in serum and PCSK9 levels might be used for population PK modeling if considered necessary and the results of population PK modeling will be reported separately from the study report.

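### Alirocumab and PCSK9 are sampled at Week 10, but the windows that govern them have no Week 10 row, so no Week 10 by-visit summary or profile point can be produced

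*SAP*

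**What the plan says.** **Collection.** SAP 4.10 lists the sampling times: "Samples of drug concentration measurements are collected at baseline (week 0), weeks 4, 8, 10, 12, and 24". Protocol Table 1 agrees, with a PK sample at Visit 5 (Week 10, Day 71). Footnote 6 in Protocol 8.1.1 says that free and total PCSK9 are measured from the PK samples.

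**Variable and windows.** SAP 4.10 continues: "Pharmacokinetic variable is the total alirocumab concentration at each time point". It then says "Alirocumab concentration, total and free PCSK9 concentration will be described following time windows as defined in" Appendix 10.2. SAP 6.5 repeats the instruction and names PK: "Data analyzed by time point (including efficacy, laboratory safety data, vital signs, ECG, quality of life, PK and ADA) will be summarized using the analysis". That sentence goes on to point to the same appendix, and the section makes its windows applicable to all analyses.

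**The windows.** Appendix 10.2 has two double-blind tables. Table 1a is headed "Analysis Windows Definition for Double-Blind Period – All Endpoints Except Vital Signs" and has rows for Weeks 4, 8 and 12 only. Table 1b is for vital signs and adds a Week 10 row.

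**Selection.** SAP 6.5: "If multiple valid values of a variable exist within an analysis window, the nearest from the targeted study day will be selected". Ties go to the later value.

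**Reporting.** SAP 5.10 says that alirocumab and PCSK9 concentrations "will be summarized on the PK population by treatment group and visit using descriptive statistics", with time-profile graphs by treatment group. Protocol 10.4.5 and 10.4.6 plan mean or median plots by time point and individual plots against actual time. SAP 5.10 makes the individual actual-time plots optional.

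**The concern.** The SAP collects a Week 10 concentration and defines the PK variable at each time point, yet its window table has nowhere to put that value. Assessing the pharmacokinetics of alirocumab 150 mg Q2W is a stated secondary objective, and the by-visit tables and profiles are its main planned output.

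Followed as written, the rules have two effects:

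- The Week 10 point disappears from the alirocumab, total PCSK9 and free PCSK9 summaries and profiles.
- When the neighbouring sample is missing, a Week 10 concentration is shown under another week. A Visit 5 sample labelled Week 12 would normally precede the Day 71 injection, because samples are drawn before dosing when visit and dosing day coincide. It would then follow five scheduled double-blind injections (Days 1, 15, 29, 43, 57), whereas a true Week 12 sample follows six.

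The omission is not declared. SAP 1.2.3 lists a single change from the statistical section of Protocol Amendment 3, the new-onset-diabetes analysis.

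**Working it through.** The plan gives no figure of its own to reproduce. The check is a count of days.

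**Inputs**

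| Item | Value | Source |
|---|---|---|
| Visit 4 (Week 8) | Day 57 ± 5, i.e. 52–62 (11 days) | Protocol Table 1 |
| Visit 5 (Week 10) | Day 71 ± 5, i.e. 66–76 (11 days) | Protocol Table 1 |
| Visit 6 (Week 12) | Day 85 ± 3, i.e. 82–88 (7 days) | Protocol Table 1 |
| Week 8 window | 43–70, target 57 | SAP Table 1a |
| Week 12 window | 71 to the smaller of 98 and the first open-label injection day, target 85 | SAP Table 1a |
| Week 10 window | 64–77, target 71 | SAP Table 1b, vital signs only |

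These are the widest visit windows in the table header; narrower ones are tested in step 4.

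**Step 1: where a Visit 5 sample falls under Table 1a.**
- Days 66–70 (5 of the 11 days) fall in Week 8. Distance from target is 66 − 57 = 9 to 70 − 57 = 13 days.
- Days 71–76 (6 of the 11 days) fall in Week 12. Distance is 85 − 71 = 14 down to 85 − 76 = 9 days.
- The nominal Day 71 falls in Week 12, 14 days from target.

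**Step 2: both neighbours present and in schedule.** The Visit 4 sample is at most 5 days from Day 57 and the Visit 6 sample at most 3 days from Day 85. The Visit 5 sample is at least 9 days from either target, so it always loses. Enumerating 11 × 11 × 7 = 847 day combinations confirms this: Visit 5 is selected in 0 of 847.

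**Step 3: a neighbour missing.**
- Visit 4 sample missing: a Visit 5 sample on Days 66–70 becomes the Week 8 value. One on Days 71–76 still loses to Visit 6.
- Visit 6 sample missing: a Visit 5 sample on Days 71–76 becomes the Week 12 value. One on Days 66–70 still loses to Visit 4.

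**Step 4: narrower visit windows.** Footnote 9 in Protocol 8.1.1 gives ± 3 days without apheresis and + 1 day with it.
- Without apheresis, Days 68–70 (3 days) go to Week 8, at 11–13 days from target, and Days 71–74 (4 days) to Week 12, at 11–14 days.
- With apheresis, Days 71–72 both go to Week 12, at 13–14 days.

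The split changes; the pattern does not.

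**Step 5: the same visits under Table 1b.** With Week 8 = 43–63, Week 10 = 64–77 and Week 12 from 78, all 11 Visit 5 days map to Week 10. The sample is kept there in 847 of 847 combinations, and it takes no value from Week 8 or Week 12.

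**Size.** The planned post-baseline double-blind samples are Weeks 4, 8, 10 and 12, so one in four (25%) is affected. At full attendance of 74 patients randomized 2:1, that is 74 × 2/3 ≈ 49 samples on alirocumab and 74 × 1/3 ≈ 25 on placebo.

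**The case against.** **The omission may be deliberate.** Time point is the column label in the Appendix 10.2 tables, so SAP 4.10 can be read as meaning each analysis time point, with its first sentence describing collection only. The SAP also uses Weeks 4, 8 and 12 for the LDL-C model, the residual checks, the missing-data patterns and the lipid summaries. This reading is possible. It still leaves a scheduled sample with no stated use in the by-visit output, and it does not remove the mislabelling in step 3.

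**By visit could mean nominal visit.** A programmer might read SAP 5.10 that way and produce a Week 10 column. But SAP 4.10 and 6.5 both direct PK to the windows, so the text does not support that reading.

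**The consequences are small.** This stands. PK and PCSK9 output is descriptive, Weeks 4, 8, 12 and 24 remain, and Week 10 is another planned pre-dose sample on the same fixed dose. Nothing in the documents shows that a PK conclusion would change.

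**A reader might infer that every Week 10 concentration is discarded, or never enters a by-visit summary.** The documents do not support that. A value with no nearer neighbour in its window is kept, under the wrong week. All values also remain available for individual actual-time plots, planned in the protocol and optional in the SAP, and for population PK modelling if it is done. Those uses need no windows. The fallback is limited, however: under the SAP neither use is mandatory.

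**Borrowing Table 1b has a cost.** This also stands, and is set out with the fix.

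**Conclusion.** The point holds in this form: the SAP as written cannot produce a Week 10 summary or mean/median profile point for total alirocumab, total PCSK9 or free PCSK9, although all three are sampled then. The Week 10 value leaves the by-visit output when the in-schedule Week 8 or Week 12 sample in its window exists, and is reported under that week when it does not.

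The size is one of four planned post-baseline double-blind samples per patient, about 74 samples per analyte at full attendance. Three assumptions matter:

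- The sample counts assume that all 74 patients attend.
- The 0 of 847 result assumes that Visits 4 and 6 are within their protocol windows. A neighbour drawn far off schedule could lose to the Week 10 sample, which would again be mislabelled.
- Table 1a is taken to govern PK and PCSK9, as its title and SAP 6.5 say.

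The effect is confined to descriptive PK and pharmacodynamic output. No hypothesis test, alpha allocation or power figure changes through this point, and it should not be read as a finding about the LDL-C analysis. It is worth correcting because it affects a secondary objective and the remedy is already in the SAP.

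**What to change.** In SAP 4.10 and Appendix 10.2, state that total alirocumab and total and free PCSK9 use the Table 1b windows:

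- Week 4: Days 15–42
- Week 8: Days 43–63
- Week 10: Days 64–77
- Week 12: Day 78 to the smaller of 98 and the first open-label injection day

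Retitle Table 1a to exclude these concentrations and Table 1b to include them.

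If the sponsor does intend Week 10 samples only for actual-time plots or modelling, the minimum is to say so in SAP 4.10, exclude them from the Week 8 and Week 12 windows, and restore the actual-time plots to a firm commitment as in Protocol 10.4.5 and 10.4.6.

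**Cost.** A wording change and one window assignment in the PK programs before the first-step database lock; no new data. There are two small downsides:

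- The PK/PCSK9 Week 12 window would start at Day 78 while that for LDL-C starts at Day 71. Any concentration-versus-efficacy plot should carry a note.
- A patient whose only late sample falls on Days 71–77 would no longer have a Week 12 PK value. The sample would be shown as Week 10, which describes it better.
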